# 6. ELIGIBILITY CRITERIA

#### 6.1. INCLUSION CRITERIA

- Adult Patients (≥18 years) affiliated to a social insurance protection regimen.
- Patients with moderate to severe chronic ( $\geq 6$  months) hand eczema with an Investigator global assessment (IGA) of 3 or 4 (out of a scale of 0 to 4).
- Patients intolerant (according to the physician) or resistant to highly potent topical corticosteroids. Inadequate response (resistance) to highly potent topical corticosteroids is defined as a history of failure to achieve and maintain remission or a low disease activity state (comparable to an IGA score of 0 [indicating clear] to 2 [indicating mild]) despite treatment with a daily regimen of highly potent topical corticosteroids applied for 14 days or for the maximum duration recommended for highly potent topical corticosteroids.
- Patients who are able to understand the study procedures including the ability to complete patientoriented questionnaires.
- Patients who are able to apply a stable dose of emollients within 7 days before the baseline visit.
- Patients who agree to sign the written informed consent.

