#### 10. JUDGEMENT CRITERIA

#### 10.1. MAIN JUDGEMENT CRITERION

- The primary outcome measure will be the 16-week percent change since baseline of the severity score mTLSS (modified Total Lesion Symptom Score).
- The mTLSS combines an evaluation of hand eczema lesions severity including 6 key signs (erythema, desquamation, lichenification/hyperkeratosis, vesiculae, oedema, fissures) and the intensity of pruritus and pain.

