#### 10.2. SECONDARY JUDGEMENT CRITERIA

- Evolution of pruritus associated with CHE at week 16 since baseline measured with a visual analog scale.
- Evolution of pain associated with CHE at week 16 since baseline measured with a visual analog scale.
- Improvement of quality of life at week 16 since baseline measured by DLQI (Dermatology Life Quality Index) and EQ-5D.
- Evolution of sleep loss associated with CHE at week 16 since baseline measured with a visual analog scale.
- Clearance or almost clearance of hand eczema at week 16 as defined by an Investigator's global assessment (IGA) of 0 or 1.
- Clearance or almost clearance of hand eczema at week 16 as assessed by the Patient's global assessment (PaGa) of 0 or 1.
- Improvement of work productivity at week 16 since baseline as assessed by the WPAI questionnaire (Work Productivity and Activity Impairment).
- Evolution of the Eczema Area and Severity Index at week 16 since baseline in patients who have eczema on other parts of the body than the hands.
- The safety throughout the course of the study (at 20 weeks since baseline) by monitoring adverse events, serious adverse events, injection site reactions.
- The evolution of laboratory parameters (full blood count, total IgE and specific IgE) at week 16 since baseline.

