# PHYSICAL EXAMINATION AND INVESTIGATOR ASSESSMENTS

• Modified TLSS (21, 22): The seven individual CHE symptoms; (erythema, scaling, lichenification or hyperkeratosis, vesiculation, edema, fissures, and pruritus/pain) form the composite scale of mTLSS' strength and each one of them scores from 0 (mild) to 3 (severe). The scores are summed, extending from a base estimation of 0 (no signs or symptoms) to the most extreme of 21 (more serious disease).

Symptoms	Severity, morphological description								
erythema	$\Box$ 0 = none								
	□ 1 = mild erythema								
	$\Box$ 2 = redness								
	$\Box$ 3 = deep/dark red erythema								
scaling	$\Box 0 = \text{none}$								
	$\Box$ 1 = mild fines scales, limited area								
	$\Box$ 2 = thicker scales, extended area								
	$\Box$ 3 = thick scales on more than 30% of the hand								
lichenification	$\Box$ 0 = none								
	$\Box$ 1 = mild thickening, limited area								
	$\Box$ 2 = moderate thickening, extended area								
	$\Box$ 3 = severe thickening, extended area								
Skin vesicles	$\Box$ 0 = none								
	$\Box$ 1 = vesicles on less than 10% of the hand								
	$\Box$ 2 = vesicles on 10 to 30% of the hand								
	$\Box$ 3 = vesicle on more than 30% of the hand								
oedema	$\Box$ 0 = none								
	$\Box$ 1 = mild oedema, on less than 10% of the hand								
	$\Box$ 2 = oedema on more than 10% of the hand								
	$\Box$ 3 = oedema and induration on extended area								
cracking	$\Box$ 0 = none								
	$\Box$ 1 = craking on a small part of the hand								
	$\Box$ 2 = painful craking on multiple hand area								
	$\Box$ 3 = deep/dark red erythema								
Pruritus / pain	$\Box$ 0 = none								
	$\Box$ 1 = mild discomfort several times a day								
	$\Box$ 2 = recurring discomfort during the day								
	$\Box$ 3 = persistent discomfort leading to sleep disorder								

Investigator's Global Assessment (IGA): IGA is a global assessment of the patient's overall severity of their CHE, based on a static, numeric 5-point scale from 0 (clear skin) to 4 (severe disease). The score is based on an overall assessment of the degree of erythema, papulation/induration, oozing/crusting, and lichenification. The assessment will be based on the condition of the disease at the time of evaluation and not in relation to the condition at previous visit.

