# **Investigator's Global Assessment**

Score	Disease severity	Standard IGA Scale	IGA morphological descriptors
0	Clear	No inflammatory signs of	No erythema and no elevation
		CHE	(papulation/infiltration)
1	Almost clear	Just perceptible erythema	Barely perceptible erythema
		and just perceptible	and/or minimal lesion elevation
		papulation/infiltration	(papulation/infiltration) that is
			not widespread
2	Mild disease	Mild erythema and mild	Visibly detectable, light pink
		papulation/infiltration	erythema and very slight
			elevation (papulation/infiltration)
3	Moderate disease	Moderate erythema and	Dull red, clearly distinguishable
		moderate	erythema and clearly perceptible
		papulation/infiltration	but not extensive elevation
			(papulation/infiltration)
4	Severe disease	Severe erythema and	Deep/dark red erythema, marked
		severe	and extensive elevation
		papulation/infiltration	(papulation/infiltration)

• EASI: The EASI assesses extent of disease at 4 body regions and measures 4 clinical signs: (1) erythema, (2) induration/papulation, (3) excoriation, and (4) lichenification each on a scale of 0 to 3. The EASI confers a maximum score of 72. The EASI evaluates 2 dimensions of AD:disease extent and clinical signs (23). To be performed only if CHE is associated with AD.

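### The IGA text and its grade table name different signs, and neither names scaling, vesicles, oedema or fissures, so IGA 0/1 need not mean clear or almost clear hands

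*Protocol*

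**What the plan says.** The IGA has two formal roles. Section 6.1 admits patients with "hand eczema with an Investigator global assessment (IGA) of 3 or 4". Section 10.2 lists as a secondary criterion "Clearance or almost clearance of hand eczema at week 16 as defined by an Investigator's global assessment (IGA) of 0 or 1".

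Section 11.4 describes the scale twice. The text introduces it broadly, "IGA is a global assessment of the patient's overall severity of their CHE", and then lists its content: "The score is based on an overall assessment of the degree of erythema, papulation/induration, oozing/crusting, and lichenification". The table headed Investigator's Global Assessment gives the descriptors for each grade. Grade 1 starts from "Barely perceptible erythema" with minimal elevation. Grade 4 starts from "Deep/dark red erythema, marked" and extensive elevation. Grades 1 to 4 are anchored on redness and papulation/infiltration and nothing else. Grade 0 carries a general phrase about the absence of inflammatory signs of CHE, but its morphological column again names only erythema and elevation.

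For the primary score, section 10.1 names "6 key signs (erythema, desquamation, lichenification/hyperkeratosis, vesiculae, oedema, fissures", together with pruritus and pain. Section 11.4 scores the mTLSS on seven items from 0 to 3, for a maximum of 21.

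**The concern.** Two descriptions of one scale give assessors two rules. An assessor who follows the text weighs four signs; one who follows the table weighs two. The same hands can then receive different grades at different centres.

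Both descriptions also leave out signs that the protocol itself treats as central to hand eczema. This matters in three places:

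- **Response.** Section 4.2 speaks of clearance or almost clearance of CHE, but the anchors describe loss of redness and infiltration. Fissures and scale can persist in a patient counted as a responder.
- **Entry.** Grade 3 requires plainly visible redness and elevation. Hands that are mainly scaling and fissured may not reach it, and section 6.1 has no mTLSS threshold as an alternative route. Section 6.1 also uses IGA 0 to 2 as the benchmark for resistance to topical corticosteroids. Section 13.3 treats only mild disease at baseline as a major violation for the Per-Protocol set, and mild is the table's label for grade 2.
- **Conclusion.** Section 3.5 expects a statement about moderate to severe hand eczema in general.

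**Working it through.** **The plan's own figure.** Section 13.1 gives a difference of 25 percentage points, SD 40, two-sided alpha 0.05 and 42 per group. The normal approximation is n = 2 × (1.960 + 0.842)² × 40²/25² = 40.2, so 41 per group. The exact two-sample t-test needs 41.2, so 42, and has 80.8% power at 42. Adding 10% non-evaluable gives 84/0.90 = 93.3, so 94. The plan reproduces. It rests on the mTLSS, so nothing below changes it.

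**Sign by sign.** The first column comes from section 10.1, the others from section 11.4.

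| Key sign | IGA text | IGA table, grades 1 to 4 | mTLSS maximum |
|---|---|---|---|
| Erythema | named | named | 3 |
| Scaling (desquamation) | no | no | 3 |
| Lichenification/hyperkeratosis | lichenification named | no | 3 |
| Vesicles | no | no | 3 |
| Oedema | no | no | 3 |
| Fissures (cracking) | no | no | 3 |

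The text covers 2 of the 6 signs and the table covers 1. Four appear in neither. Those four carry 4 × 3 = 12 of 21 mTLSS points (57%). Oozing/crusting and lichenification are in the IGA text but in no grade of the table; that is the internal mismatch.

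**What grade 1 can hold.** Take the table's anchors at face value and consider a patient with faint redness and no lesion elevation.

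1. Scaling 3 (thick scale over more than 30% of the hand) conflicts with nothing in the grade 1 descriptor.
2. Cracking 2 (painful, in several areas) also conflicts with nothing. Cracking 3 is not used, because its printed anchor repeats the erythema grade 3 wording and so cannot sit with faint redness.
3. Vesicles and oedema are set to 0, because an assessor might read them as elevation.
4. The sum from these two signs is 3 + 2 = 5, and 5/21 = 24%.
5. If mTLSS erythema 1 is taken to match the grade 1 redness descriptor (an assumption), the sum is 6, and 6/21 = 29%.

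This patient fits the table's almost clear grade. At baseline the same hands would not meet the grade 3 anchor.

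**How many patients.** The protocol gives no data on agreement between IGA and mTLSS, so no proportion can be computed.

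**The case against.** The strongest reply is that this is a global assessment. Investigators are told to rate overall CHE severity, the grade labels are plain words, and grade 0 refers to inflammatory signs of CHE in general. A dermatologist would hardly call thickly scaled, painfully cracked hands almost clear. This stands in part: the misgrading is permitted by the anchors, not compelled by the protocol. It does not remove the problem, because grade 1 is where response is decided and it has no anchor for the four unnamed signs. The outcome then depends on how far each assessor departs from the written descriptors.

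Scope is also limited. The primary endpoint scores all six signs. IGA 0/1 serves one of nine secondary objectives, is tested without multiplicity adjustment, and is reported beside the patient's own global assessment.

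A reader might go further in four ways that the documents do not support:

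- **That the IGA as a whole grades only erythema and papulation.** This is true of table grades 1 to 4. The text also lists oozing/crusting and lichenification.
- **That hyperkeratotic disease is shut out at entry.** This is not shown. The text includes lichenification, which the mTLSS pairs with hyperkeratosis.
- **That a responder can still be severe on the primary score.** The protocol defines no mTLSS severity bands.
- **That a responder can hold 3 + 3 + 3 = 9 of 21 points (43%) from scaling, cracking and pruritus/pain.** This uses cracking 3, whose printed anchor conflicts with faint redness. It also counts a symptom item that is not among the six signs.

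Finally, recruitment began in July 2019 and version 6.0 is dated June 2023, about 47 months into a 54-month inclusion period. Rewriting the scale now could put early and late patients on different scales. That objection is sound and shapes the fix.

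**Conclusion.** The point holds as an inconsistency within the protocol and a limit on what the clearance endpoint can support. The IGA text and table must be reconciled, and IGA 0/1 cannot by itself carry a claim of clear or almost clear hands. The illustration of 5 to 6 of 21 mTLSS points in a grade 1 patient shows what the anchors allow; it is not an estimate of how often this happens. It assumes that the table is followed as written and, for the upper figure, that mTLSS erythema 1 corresponds to the grade 1 redness descriptor. Possible loss of patients with little redness at entry affects the description of the population, again by an unknown amount. The primary analysis and sample size stand.

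**What to change.** 1. Keep IGA 0/1 as the stated secondary endpoint. Reconcile the section 11.4 text with its table and record which description sites have used. Do not alter the scale mid-trial unless earlier scores are reconciled with it.
2. Before unblinding, prespecify a supportive responder analysis: IGA 0 or 1 and each of the six mTLSS sign items at 0 or 1 at Week 16, analysed with the same stratified Cochran-Mantel-Haenszel method and ITT population as IGA 0/1. The cut-off is a choice made here, not one found in the protocol, so it should remain supportive.
3. Tabulate the six mTLSS sign items at Week 16 among IGA 0/1 responders, by group. This shows directly how often scale, vesicles, oedema or fissures persist.
4. Reconcile the mTLSS cracking grade 3 anchor, which repeats the erythema wording, since that item feeds the supportive analysis and also the primary score.
5. Word the clearance conclusion and the population description to match what the IGA anchors grade.

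The mTLSS is already scored at Week 16 (visit 9), so no visit or assessment is added. Section 13.2 has the SAP validated before unblinding, so the rule can be fixed blind. The cost is one more analysis. Its response rate cannot exceed that for IGA 0/1 and will probably be somewhat lower in both arms.

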# **Investigator's Global Assessment**

Score	Disease severity	Standard IGA Scale	IGA morphological descriptors
0	Clear	No inflammatory signs of	No erythema and no elevation
		CHE	(papulation/infiltration)
1	Almost clear	Just perceptible erythema	Barely perceptible erythema
		and just perceptible	and/or minimal lesion elevation
		papulation/infiltration	(papulation/infiltration) that is
			not widespread
2	Mild disease	Mild erythema and mild	Visibly detectable, light pink
		papulation/infiltration	erythema and very slight
			elevation (papulation/infiltration)
3	Moderate disease	Moderate erythema and	Dull red, clearly distinguishable
		moderate	erythema and clearly perceptible
		papulation/infiltration	but not extensive elevation
			(papulation/infiltration)
4	Severe disease	Severe erythema and	Deep/dark red erythema, marked
		severe	and extensive elevation
		papulation/infiltration	(papulation/infiltration)

• EASI: The EASI assesses extent of disease at 4 body regions and measures 4 clinical signs: (1) erythema, (2) induration/papulation, (3) excoriation, and (4) lichenification each on a scale of 0 to 3. The EASI confers a maximum score of 72. The EASI evaluates 2 dimensions of AD:disease extent and clinical signs (23). To be performed only if CHE is associated with AD.

# **Calculation of the EASI**

Body region	Erythema	Induration/ papulation	Excoriation	Lichenification	Area score	Weighting factor	Score
Head/neck	SS	SS	SS	SS	x AS	x 0.1	
Trunk	SS	SS	SS	SS	x AS	x 0.3	
Upper extremities	SS	SS	SS	SS	x AS	x 0.2	
Lower extremities	SS	SS	SS	SS	x AS	x 0.4	
	The EASI score is the sum of the 4 body region scores Range 0-72				Range 0-72		

AS: area score; EASI: Eczema Area and Severity Index; SS: Severity Score

#### EASI severity score scale and area score scale

Severity score scale		
0	None/absent	
1	Mild	
2	Moderate	
3	Severe	

Area score scale		
0	0% affected area	
1	1% to 9% affected area	
2	10% to 29% affected area	
3	30% to 49% affected area	
4	50% to 69 affected area	
5	70% to 89% affected area	
6	90% to 100% affected	
	area	

# PATIENT QUESTIONNAIRES

- Patient's Global Assessment (PGA): The PGA is a single-item question asking the patient how they would rate their overall CHE symptoms over the past 24 hours. The 5 categories of responses range from "no symptoms" (0) to "severe." (4)
- DLQI: The Dermatology Life Quality Index (DLQI) is a simple, patient-administered, 10-item, validated, quality-of-life questionnaire that covers 6 domains including symptoms and feelings, daily activities, leisure, work and school, personal relationships, and treatment. The recall period of this scale is over the "last week." Response categories include "not at all," "a lot," and "very much," with corresponding scores of 1, 2, and 3, respectively, and unanswered ("not relevant") responses scored as 0. Scores range from 0-30 with higher scores indicating greater impairment of quality of life. A DLQI total score of 0 to 1 is considered as having no effect on a patient's health-related QoL (24), and a 4-point change from baseline is considered as the minimal clinically important difference threshold (25; 26).
- EQ-5D-5L: The European Quality of Life–5 Dimensions–5 Levels (EQ-5D-5L) is a standardized measure of health status that provides a simple, generic measure of health for clinical and economic appraisal. The EQ-5D-5L consists of 2 components: a descriptive system of the respondent's health and a rating of his or her current health state using a 0 to 100 mm VAS. The descriptive system comprises the following 5 dimensions: mobility, self-care, usual activities, pain/discomfort, and anxiety/depression. Each dimension has 5 levels: no problems, slight problems, moderate problems, severe problems, and extreme problems. The respondent is asked to indicate his or her health state by ticking (or placing a cross) in the box associated with the most appropriate statement in each of the 5 dimensions. It should be noted that the numerals 1 to 5 have no arithmetic properties and should not be used as an ordinal score. The VAS records the respondent's self-rated health on a vertical VAS where the endpoints are labeled "best imaginable health state" and "worst imaginable health state." This information can be used as a quantitative measure of health outcome. The EQ-5D-5L health states, defined by the EQ-5D-5L descriptive system, may be converted into a single summary index by applying a formula that essentially attaches values (also called weights) to each of the levels in each dimension (27)
- Hand eczema Pruritus VAS: The hand eczema pruritus VAS is a patient administered single item scale designed to measure current pruritus from CHE using a 100 mm horizontal VAS. Overall severity of a patient's pruritus from CHE is indicated by placing a single mark on the horizontal scale (0 = none; 100 = as severe as you can imagine)
- hand eczema Pain VAS: The hand eczema pain VAS is a patient administered single item scale designed to measure current pain from CHE using a 100 mm horizontal VAS. Overall severity of a patient's pain from CHE is indicated by placing a single mark on the horizontal scale (0 = none; 100 = as severe as you can imagine)

- hand eczema Sleep loss VAS: The hand eczema sleep loss VAS is a patient administered single item scale designed to measure current sleep loss from CHE using a 100 mm horizontal VAS. Overall severity of a patient's sleep loss from CHE is indicated by placing a single mark on the horizontal scale (0 = no sleep loss; 100 = as severe as you can imagine).
- WPAI questionnaire: The work productivity and activity impairment questionnaire-atopic dermatitis (WPAI) records impairment due to CHE during the past 7 days. The WPAI-AD consists of 6 items grouped into 4 domains: absenteeism (work time missed), presenteeism (impairment at work/reduced on-the-job effectiveness), work productivity loss (overall work impairment/absenteeism plus presenteeism), and activity impairment. Scores are calculated as impairment percentages (28), with higher scores indicating greater impairment and less productivity.
- Perform randomization (for details see page 30) and give subject treatment instructions to the patient
- Administer study drug (sub cutaneous injection of the first dose of dupilumab or placebo): site staff will perform the first injection and will explain to patient how to perform self-injection and will stay with him for the first self injection (second injection)
- Monitor the patient for 1 hour after the SC injection: vital signs and AE assessment (for details see page 30) should be done at 1 hour post-injection (+/- 10 minutes). Injection site reaction (ISR) photograph will be taken, if applicable.

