# **ECHELLE VISUELLE ANALOGIQUE DU PRURIT (EVA)**

ma	uillez préciser l'intensité globale de votre prurit (démangeaison) due à votre eczema chronique des ins au moment present en plaçant une marque sur l'échelle horizontale (0= aucune démangeaison; 100 émangeaison intense)
	0 100 Aucune Démangeaison intense
	ORK PRODUCTIVITY AND ACTIVITY IMPAIRMENT QUESTIONNAIRE: GENERAL HEALTH V2.0 (WPAI:GH) Questionnaire sur la baisse de productivité au travail et la limitation des activités: Santé générale V2.0 (WPAI :GH°)
tra syr	questions suivantes portent sur les conséquences de vos problèmes de santé sur votre capacité à vailler et à effectuer vos activités habituelles. Par problème de santé, nous entendons tout problème ou aptôme physique ou émotionnel. Veuillez, selon les questions, encercler le nombre qui convient ou appléter les espaces appropriés comme indiqué.
1)	Occupez-vous un emploi (travail rémunéré) en ce moment? NON OUI Si vous répondez NON, cochez « NON » et passez directement à la question 6.
Le	questions qui suivent portent sur les sept derniers jours , sans compter aujourd'hui.
2)	de vos problèmes de santé? Comptez les heures d'absence pour congé de maladie, les retards et départs précoces du travail, etc. dus à vos problèmes de santé. Ne comptez pas les moments où vous vous êtes absenté(e) pour participer à cette étude.
	HEURES
3)	Au cours des sept derniers jours, combien d'heures de travail avez-vous manquées pour toute autre raison que vos problèmes de santé telle qu'un congé, des vacances ou la participation à cette étude?
	HEURES
4)	Au cours des sept derniers jours, combien d'heures de travail au total avez-vous effectuées?
	HEURES (Si votre réponse est « 0 », passez directement à la question 6.)

5) Au cours des sept derniers jours, dans quelle mesure vos problèmes de santé ont-ils affecté votre productivité pendant que vous étiez en train de travailler? Tenez compte des jours pendant lesquels vous avez été limité(e) dans la quantité ou le type de travail que vous auriez pu accomplir, vous en avez fait moins que vous l'auriez souhaité ou vous ne pouviez pas travailler aussi soigneusement que d'habitude. Si vos problèmes de santé n'ont eu qu'une faible incidence sur votre travail, choisissez une note peu élevée. Choisissez une note élevée si vos problèmes de santé ont beaucoup perturbé votre travail

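### The protocol's DLQI item scores contradict its own 'no effect' band and leave 'Un peu' unscored; separately, its WPAI description does not match the form in Appendix 2

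*Protocol*

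**What the plan says.** **DLQI.** Protocol section 11.4, under Patient questionnaires, presents the DLQI as a "patient-administered, 10-item, validated, quality-of-life questionnaire". It then gives the item scores, "Response categories include 'not at all,' 'a lot,' and 'very much,' with corresponding scores of 1, 2, and 3", followed by "unanswered ('not relevant') responses scored as 0". On the total it says "Scores range from 0-30 with higher scores indicating greater impairment of quality of life", and on interpretation "A DLQI total score of 0 to 1 is considered as having no effect on a patient's health-related QoL" and "a 4-point change from baseline is considered as the minimal clinically important difference threshold".

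The French form in Appendix 2 has four graded answers: *Enormément*, *Beaucoup*, *Un peu* and *Pas du tout*. *Non concerné* is added on items 3 to 10 only. Item 7 differs: it asks *Oui*, *Non* or *Non concerné*, and after *Non* a sub-question offers *Beaucoup*, *Un peu* or *Pas du tout*. The form prints no scores.

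Section 10.2 names the DLQI as a quality-of-life measure among the secondary criteria. Section 13.4 analyses change from baseline to week 16 by covariance analysis.

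**WPAI.** Section 11.4 names the atopic-dermatitis version and says that it "records impairment due to CHE during the past 7 days". The form in Appendix 2 is headed "QUESTIONNAIRE: GENERAL HEALTH V2.0 (WPAI:GH" and asks about any physical or emotional health problem.

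**The concern.** The DLQI rule is a stated rule, not a detail left for later, and it disagrees with three things in the same protocol: the form, which has an answer the rule does not score; the band that reads a total of 0–1 as no effect; and the ordering of the answers, since two replies that both mean no impairment differ by a point. A programmer who followed section 11.4 would mis-score a named secondary endpoint, and because *Un peu* has no value, two programmers could build different totals from the same forms.

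The WPAI mismatch is one of attribution. Section 4.2 expects about half the patients to have eczema beyond the hands, section 9.1 allows comorbid asthma, and section 3.1.2 describes the cytokines that dupilumab blocks as essential in both atopic dermatitis and asthma. A difference on a general-health form could therefore partly reflect benefit outside the hands, and the section 11.4 wording would invite reporting it as specific to hand eczema.

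**Working it through.** **Inputs.** From section 11.4: 10 items; *not at all* = 1, *a lot* = 2, *very much* = 3, *not relevant* = 0; stated range 0–30; no-effect band 0–1; threshold 4 points. From Appendix 2: *Un peu* on every item (on item 7, in the sub-question); *Non concerné* on items 3–10 only; item 7 has *Oui* in place of *Enormément*. No score is given for *Un peu* or for *Oui*.

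**1. Can the stated range be reproduced?** Total = sum of the ten item scores.
- Lowest total on a completed form from the scored answers: items 1 and 2 cannot be marked not relevant, so 2 × 1 + 8 × 0 = 2.
- Highest total: 10 × 3 = 30 if item 7 *Oui* is taken as 3; otherwise 9 × 3 + 2 = 29.

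The rule gives 2–30 or 2–29, not 0–30. A total of 0 or 1 would need skipped items, or a value for *Un peu* low enough to rank it below *not at all*.

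**2. Score of an unimpaired patient.** With *k* of items 3–10 marked not relevant and the rest *not at all*, total = 10 − *k*, with *k* from 0 to 8. That gives 10 when all ten items are answered *Pas du tout*, down to 2. Every value lies above the 0–1 band.

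**3. Switching between two unimpaired answers.** *Not at all* to *not relevant*: 1 − 0 = 1 point of apparent improvement per item.

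**4. Change scores, literal rule against 0/1/2/3 coding.** In the second row item 7 uses *Oui* = 3.

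| Shift | Literal | 0/1/2/3 |
|---|---|---|
| *a lot* to *not at all*, per item | 2 − 1 = 1 | 2 − 0 = 2 |
| *very much* to *not at all*, all ten items | 10 × (3 − 1) = 20 | 10 × (3 − 0) = 30 |
| *very much* to *a lot*, per item | 3 − 2 = 1 | 3 − 2 = 1 |

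Reaching 4 points by *a lot* to *not at all* shifts takes 4 ÷ 1 = 4 items under the literal rule and 4 ÷ 2 = 2 items under the other.

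**5. Sensitivity to the missing *Un peu* score.** The values 0, 1 and 1.5 are assumptions, since the protocol gives none. Points of improvement per item:

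| Shift | *Un peu* = 0 | = 1 | = 1.5 | 0/1/2/3 coding |
|---|---|---|---|---|
| *a little* to *not at all* | −1 | 0 | 0.5 | 1 |
| *a lot* to *a little* | 2 | 1 | 0.5 | 1 |
| *very much* to *a little* | 3 | 2 | 1.5 | 2 |

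Depending on that value, some shifts are shrunk, some unchanged, some enlarged and one reversed in sign.

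**6. Which coding fits the rest of the protocol?** Keep the stated 3 and 2 for the two highest answers. A no-effect band of 0–1 requires *not at all* = 0. The only whole number left between 0 and 2 is 1, for *a little*. The minimum is then 0. The maximum is 9 × 3 + 2 = 29 if *Oui* has no score, and 9 × 3 + 3 = 30 if *Oui* = 3. So *Oui* = 3 is needed to reproduce 0–30.

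**7. WPAI, text against form.** Version: atopic dermatitis in section 11.4, General Health V2.0 in Appendix 2. Attribution: hand eczema in section 11.4, any health problem in Appendix 2. Sections 4.2 and 10.2 speak only of work productivity, without tying it to hand eczema, whereas pruritus, pain and sleep loss are each tied to it. The conflict is between section 11.4 and the form; the objective and endpoint fit the form.

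**The case against.** The strongest reply is that this is a drafting slip with no demonstrated effect. The protocol calls the instrument validated, gives the range as 0–30 and reads 0–1 as no effect, so the intended scoring can be recovered. The list of categories is introduced in a way that need not be exhaustive. The form prints no scores, so if the ticked category is stored, any error can be put right at analysis. Nothing in the protocol shows that the eCRF or an analysis program uses the 1/2/3 coding.

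Most of that stands, and it makes the harm conditional on the rule being followed. It does not clear the text: even if the list is incomplete, scoring *not at all* as 1 still breaks the 0–1 band. Nor is this a detail deferred to the SAP. For secondary endpoints section 13.4 defers missing-data methods, not instrument scoring.

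Two stronger readings are tempting and unsupported. One is that the quality-of-life effect would be compressed by a third or a half. Those figures describe selected shifts (20 against 30 points; 1 against 2 per item), not a between-group mean, and the net effect turns on the unstated *Un peu* value. The other is that every form would be mis-scored; one with only *a lot* and *very much* answers scores the same either way, item 7 *Oui* apart. The protocol also describes no analysis using the 4-point threshold, so its altered meaning affects interpretation only.

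On the WPAI, a reader might infer that the endpoint itself is wrong. It is not: the objective and endpoint claim work productivity in general, and a randomised comparison on the general-health form is valid for that.

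**Conclusion.** The DLQI rule is wrong as written. Taken literally, it gives an unimpaired patient who completes the form 2 to 10 points, counts a switch between two unimpaired answers as a 1-point change, halves the *a lot* to *not at all* step, and leaves one answer on every item without a score. The total of 10 assumes that all ten items are answered *Pas du tout*. The overall bias in the change from baseline cannot be stated from the protocol.

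The reach is limited to the DLQI, a secondary endpoint tested without multiplicity adjustment. The primary endpoint and the sample size rest on the mTLSS and are unaffected. Damage follows only if section 11.4 is implemented as it stands, which the protocol neither shows nor rules out.

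The WPAI mismatch is real but separate and smaller: the section 11.4 description is wrong for the form supplied, and the objective and endpoint need no change.

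**What to change.** **DLQI.** Replace the scoring sentence in section 11.4 with: *Pas du tout* 0, *Un peu* 1, *Beaucoup* 2, *Enormément* 3, *Non concerné* 0, and item 7 *Oui* 3. Check that the eCRF or analysis derivation uses this coding, and do so before unblinding, because a scoring change made afterwards would look data-driven.

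**WPAI.** Rewrite the section 11.4 description to match the WPAI:GH V2.0 form in Appendix 2, that is, impairment due to any health problem. Do not report the result as specific to hand eczema. Leave sections 4.2 and 10.2 as they are.

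**Cost.** Two text corrections and one check of a derivation. There is no added burden for patients and no change to the primary analysis or the sample size. The WPAI result is described a little less specifically.
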